Justification for use of E-CPT-C: This intervention will be used for the following reasons: (1) CPT-C with modification is able to provide an integrative intervention throughout treatment; (2) both CPT and CPT-C have been effectively adapted for use in veterans, and are part of a national dissemination project; and (3) most importantly, the efficacy of CPT has been established in four separate randomized controlled trials.

Confirmation of self reported alcohol use: Ethyl glucuronide (EtG) (B,T,F) provides a sensitive and reliable biomarker of recent alcohol consumption and is detectable in urine for up to three days after drinking depending upon the amount consumed (Jatlow and O'Malley 2010; Sarkola et al 2003; Wurst et al 2006; Wurst et al 2004). Comparison of urine EtG levels during treatment at weeks 4, 8, 12 with baseline values will provide a quantitative approximation of relative changes in alcohol exposure. For other time-points, EtG concentrations will be assayed only if a veteran self-reports abstinence or no heavy drinking and will be used in secondary analyses of composite outcomes based on self-report confirmed by EtG. Heavy exposure to non-beverage sources of ethanol such as some mouthwashes and hand washes, particularly the latter, can confound interpretation of urinary EtG assays and will be monitored. Normalization to urine creatinine concentration will correct for extremes in urinary dilution.

Research Objectives:

Specific Primary Aim # 1: To determine if zonisamide is more effective than placebo in decreasing alcohol use when used in combination with E-CPT-C in veterans with PTSD and comorbid alcohol dependence.

1a. We hypothesize that zonisamide will be more effective than placebo when used in combination of E-CPT-C, in reducing heavy drinking days measured by the Timeline Follow-back Method (TLFB).

1b. We hypothesize that zonisamide will be more effective than placebo when used in combination of E-CPT-C, in reducing drinks per week as measured by the Timeline Follow-back Method (TLFB).

1c. We hypothesize that zonisamide will be more effective than placebo when used in combination of E-CPT-C, in reducing craving for alcohol using the Obsessive Compulsive Drinking Scale (OCDS).

Exploratory Aim #1: To determine if the combination of zonisamide with E-CPT-C is more effective than placebo in reducing symptoms of PTSD. PTSD symptoms will be assessed weekly using the PCL, and biweekly using the CAPS.

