Table 1. Summary of Weekly Study Assessments

Assessments	0	1	2	3	4	5	6	7	8	9	10	11	12	13	14	25
SCID I	x															
TLFB	x	x	x	x	x	x	x	x	x	x	x	x	x	x	x	x
OCDS		x	x	x	x	x	x	x	x	x	x	x	x	x	x	x

ADS	x														
Demographics	x														
CIWA	x														
CAPS Dx	x														
CAPS Sx		x		x		x		x		x		x		x	x
HAMD		x	x	x	x	x	x	x	x	x	x	x	x	x	x
PCL-C		x	x	x	x	x	x	x	x	x	x	x	x	x	x
SAFTEE		x	x	x	x	x	x	x	x	x	x	x	x	x	x
Independent Psychiatric Exam	x														
Physical Examination	x														
Medication Count		x	x	x	x	x	x	x	x	x	x	x	x	x	x
EKG	x														
Medical History	x														
Labs	x				x			x				x			x
UTOX	x	x	x	x	x	x	x	x	x	x	x	x	x	x	x

Data Analysis:

Descriptive statistics and graphs will be used to summarize the data on all randomized veterans. All continuous variables will be examined for adherence to the normal distribution using normal probability plots and Kolmogorov-Smirnov tests. Transformations will be applied if needed. If normality is not satisfied and transformations do not help with achieving normality alternative analytic strategies will be considered such as generalized estimating equations (GEE) or nonparametric methods for repeated measures analysis (Brunner et al 2002). For the primary hypotheses we will use mixed effects models to assess change in alcohol consumption and craving over time. Study medication (zonisamide vs placebo) and time (in weeks and months) will be used as a within-subject factors. The primary outcome drinking variable will be heavy drinking days and drinks per week calculated from the timeline data.

If significant differences between groups are observed Bonferroni adjusted post-hoc tests will be performed to test group differences at each time point. The same model will be used to examine changes in craving (using the OCDS) and PTSD symptoms (using the PCL every week and the CAPS every two weeks) over time.

XII. Labeling and Storage of Data and Specimens

All data and blood specimens will be stored without direct identifiable information, but will be identifiable via a linking code. Blood will not be used for the purpose of establishing cell lines. Any hard copy records associated with the study will be kept in locked offices. The secured research records are labeled with code numbers only (names and other identifying information are kept separate from research records). Access to hard copy data is only given to

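### The primary analysis of heavy drinking days hangs on a normality check with an open-ended fallback, and weekly 0-7 counts are likely to fail that check

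*Combined protocol and SAP*

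**What the plan says.** The sequence is in Section XI, Data Analysis. "All continuous variables will be examined for adherence to the normal distribution using normal probability plots and Kolmogorov-Smirnov tests". Then "Transformations will be applied if needed". If normality still fails, "alternative analytic strategies will be considered such as generalized estimating equations (GEE) or nonparametric methods for repeated measures analysis". The default follows: "For the primary hypotheses we will use mixed effects models to assess change in alcohol consumption and craving over time". The outcome is stated as: "The primary outcome drinking variable will be heavy drinking days and drinks per week calculated from the timeline data". The time unit is left double: "time (in weeks and months) will be used as a within-subject factors".

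The section does not give:
- a level for the Kolmogorov-Smirnov (KS) test, or whether it is applied to pooled values, values at each visit or model residuals (the wording speaks of variables);
- the transformations to be tried;
- a rule for choosing between GEE and a nonparametric method, a GEE link or distribution, or a small-sample correction;
- any statement that the check is made without knowledge of treatment arm.

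No heavy-drinking rate or expected distribution appears anywhere in the document.

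**The concern.** Heavy drinking days in a week is a bounded count with eight possible values, and many of them may be zero. Such a variable is a poor candidate for a normality test, and no monotone transformation removes a spike at zero. If the check fails, the written rule moves the analysis from a named model to an open list, and the choice from that list is made with outcome data in hand.

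Two things are at stake. The estimand changes with the path: a mean difference from the linear mixed model, a difference in logs after transformation, a rate ratio from a log-link GEE, or a rank effect from a nonparametric method. This happens even if nobody acts in bad faith. Second, if the person choosing can see the arm comparison, the 5% error rate is no longer assured.

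**Working it through.** **Inputs.** The target is 100 veterans (Overview; Section IX), although Experimental subjects says fifty. Allocation is 3:1, which gives 75:25 at 100 and 37.5:12.5 at 50, taken as 38:12. Treatment lasts 12 weeks, with daily drinking from the TLFB. A heavy-drinking threshold appears only in inclusion criterion 4 and makes each day 0 or 1. A week therefore gives 0-7, 28 days 0-28 and 84 days 0-84. There is no stated figure to reproduce.

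**Step 1: a bound by hand.** If a share *s* of the sample sits on one value, the KS distance from any continuous distribution is at least *s*/2. A 0-7 count has eight values, so the largest share is at least 1/8 and the distance at least 1/16 = 0.0625, on any transformed scale. The large-sample 5% critical value is √(ln(2/0.05)/2)/√n = 1.358/√n.
- Pooled person-weeks: 100 × 12 = 1,200 gives 0.039, and 50 × 12 = 600 gives 0.055. Both are below 0.0625, so the check fails at any drinking rate. With dropout this still holds above (1.358/0.0625)² ≈ 472 person-weeks.
- One week: the critical value is 0.136 at n = 100 and 0.192 at n = 50. Failure is assured only if one value holds more than about 27% or 38% of subjects.
- One 28-day count: 29 values give a distance of at least 1/58 = 0.017, which assures nothing at n = 100.

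The bound assumes a 5% level and does not apply to model residuals.

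**Step 2: simulated failure of the check.** Assumptions, none from the documents: each subject's daily heavy-drinking probability is Beta distributed with mean 0.10, 0.20, 0.35 or 0.50 (× 7 = 0.7, 1.4, 2.45 or 3.5 heavy days a week) and intra-subject correlation 0.1, 0.3 or 0.5. Weekly counts are Binomial(7, p), without dropout. Failure means rejection at 5% on all of the raw, square-root, log(x+1) and arcsine-root scales.

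| Values tested | N | Plain KS | Lilliefors |
|---|---|---|---|
| All person-weeks pooled | 100 and 50 | 1.00 | 1.00 |
| One week, mean 0.7-1.4 | 100 | 1.00 | 1.00 |
| One week, mean 2.45-3.5 | 100 | 0.03-1.00 | 0.93-1.00 |
| One week, all means | 50 | 0.00-1.00 | 0.35-1.00 |
| 28-day count | 100 | 0.00-1.00 | 0.14-1.00 |
| 84-day total | 100 | 0.00-1.00 | 0.01-1.00 |

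The share of zero weeks ran from 0.57-0.78 at mean 0.10 down to 0.03-0.21 at mean 0.50, which explains the spread for a single week.

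**Step 3: type I error from free choice, no treatment effect.** Two assumed data models were used: logit-normal (subject SD 1.8, week SD 1.0) and the Beta-binomial model above.

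| Data model and choice | 75:25 | N = 50, about 38:12 |
|---|---|---|
| Logit-normal, best of four (t on means, t on logs, GEE, rank) | 6.5-7.4% | 7.4-8.6% |
| Logit-normal, GEE-type test alone | 4.9-6.5% | 6.7-8.1% |
| Logit-normal, better of GEE-type and rank | 5.6-7.7% | 7.7-9.0% |
| Beta-binomial, each t or rank test alone | 4.4-5.8% | not available |
| Beta-binomial, GEE-type test alone | 5.3-8.3% | not available |
| Beta-binomial, best of five | 7.6-11.5% | 8.4-12.4% |

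The best-of-four row used 1,500 trials per setting and a different GEE implementation from the next two rows, which used 3,000, so these rows are not nested. Monte Carlo standard errors near 7% are √(0.07 × 0.93/1,500) = 0.7 points and √(0.07 × 0.93/3,000) = 0.5 points. A separate run of the GEE-or-rank choice gave about 6-8% and 6-11%.

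At 38:12, choosing between GEE and rank added only 0.2-1.1 points to GEE alone. The GEE's own excess over 5% was 6.7 − 5 = 1.7 to 8.1 − 5 = 3.1 points, from an uncorrected robust variance with 12 placebo subjects.

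**The case against.** The plan names a default model and a sequence (check, transform, then alternatives). It nowhere says that several models will be run and the best reported. Looking at a pooled distribution is not looking at the arm comparison, and a check made blind to arm would largely protect the error rate. Once raw and transformed scales have failed, the t-type paths are no longer open, so best-of-four and best-of-five figures include options that the rule has excluded. The document also calls the trial a pilot, which lowers the stakes of a point or two of type I error.

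Most of this stands, and it limits the claim. A reader might infer that the check almost always fails, so that the primary analysis is in practice always picked after the fact. The documents do not support that: they give no drinking rate, allow months as well as weeks, and do not fix the form of the test. A reader might also take 6-9% as the plan's error rate. It is not.

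What the objection does not remove is the gap itself. The trial is double-blind, and Section XI requires the EtG determinations to be made without knowledge of treatment condition, but Data Analysis says nothing comparable about the normality check. If counts are held not to be continuous variables, so that the check does not apply, the plan then states no distribution for its primary outcome and needs the same repair.

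**Conclusion.** The point holds in limited form. The primary analysis of heavy drinking days depends on a check of outcome data with an unranked, open fallback and no stated blinding. For weekly counts the check is likely to fail: with certainty if raw or transformed person-weeks are pooled and tested at 5%, and usually for a single week when heavy drinking is infrequent. The named mixed model may then give way, leaving test and estimand to be settled after outcome data are seen.

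Failure is not established for monthly or 12-week counts, for model residuals, or for a plain KS test on a single week at moderate drinking levels. The type I error figures (about 6-9% under the logit-normal assumptions, up to 12.4% under the Beta-binomial ones) bound what unrestricted choice could do. Part of the 38:12 excess is small-sample GEE bias that would remain with no choice at all. The plan should be changed before unblinding; nothing here shows that its result would be wrong.

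**What to change.** Before unblinding, in Section XI:

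1. Remove the normality check as a route to the primary analysis of the drinking outcomes.
2. Fix one time unit for the primary test and state the heavy-day threshold as part of the outcome definition.
3. Name one primary model per outcome, with week-0 TLFB drinking (already in Table 1) as a covariate. For example, use an overdispersed binomial mixed model with a random subject effect for heavy days out of days observed, and a negative binomial mixed model for drinks per week. A prespecified linear mixed model, or a GEE with a stated link and small-sample correction, would remove the choice equally well.
4. List the alternatives as named sensitivity analyses that cannot replace the primary result.

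The cost is a few sentences and modest programming. A count model yields an odds or rate ratio, which may need back-transforming to a mean difference. The baseline covariate may also help power: in simulation at 75:25, with an assumed baseline correlation of 0.6, power rose from about 0.60 to 0.71-0.77 with type I error near 5%.

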Fifty veterans aged 21- 65 years old, with a current Diagnostic and Statistical Manual-IV, TR (DSM-IV) diagnosis of PTSD, assessed by the Structured Clinical Interview for DSM Disorders (SCID) & Clinician Administered PTSD Scale for DSM-IV (CAPS), and alcohol dependence (assessed using Structured Clinical Interview for DSM-IV) will be enrolled.

Study Procedures:

Overview: After signing informed consent, participants will undergo an initial assessments and screening. The screening will consist of careful psychiatric and medical evaluation that will also include screening for a veteran's potential to develop alcohol withdrawal. Those veterans who need treatment for alcohol withdrawal will be referred to our detoxification clinic as a first line of treatment. Initial assessments will include a careful diagnostic evaluation completed by highly trained and experienced research personnel, as well as collection of baseline assessments of alcohol use, PTSD symptoms and other characteristics. Veterans will be randomized to zonisamide 400mg or placebo for 12 weeks. The dose and titration schedule for zonisamide was selected based on data from clinical trials and is consistent with the recommended dosing schedules. All veterans will also be enrolled in E-CPT-C therapy. Assessments will occur weekly. At each visit veterans will have an interview with a member of the research staff whom is not providing the E-CPT-C training, receive a supply of medication, and complete self-report measures. Veterans will be compensated for their participation using a schedule outlined below. There will be one follow up session 3 months after completion of treatment.

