Initial Assessments/Screening: In order to qualify for participation, veterans will complete the following: (1) Diagnostic interview with the Structured Clinical Interview for DSM Disorders (SCID I), a comprehensive psychiatric interview schedule designed to assess psychiatric disorders in adults (First et al 1996). The SCID interview schedule covers the major Axis I psychiatric disorders defined in DSM-IV. The SCID permits comprehensive assessment of substance use as well as comorbid psychiatric disorders. (2) Drinking patterns will be assessed using The TLFB method (Sobell and Sobell 1992). This will allow documentation of the degree and frequency of daily alcohol consumption and smoking pattern. (3) PTSD symptom will be assessed using the Clinician Administered PTSD Assessment (CAPS), and (4) Veterans will have a medical history and physical examination by one of the investigators, blood tests (including SMAC-20, serum gamma-glutamyl transferase (γ -GGT), CBC with differential, thyroid function tests, and TSH), urinalysis, urine toxicology, and an electrocardiogram (EKG). It is anticipated, however, that

mild to moderate elevations in liver function tests will be common in alcohol dependent subjects. Veterans with LFT abnormalities that do not exceed 3 times normal values will be included.

Study Treatments:

Medication Treatment: Zonisamide, (target 400 mg) will be titrated upward over 6 weeks. Dosing will be given once daily and veterans on placebo will be given identical number, color and consistency of capsules as those on active medication. Below is the proposed dosing schedule, although we will make adjustments if side effects occur:

Zonisamide 400mg/day

Week 1:	Days 1-7	ZON 100mg, +	= TOTAL 100mg
Week 2:	Days 1-7	ZON 200mg, +	= TOTAL 200mg
Week 3:	Days 1-7	ZON 200mg, +	= TOTAL 200 mg
Week 4:	Days 1-7	ZON 300mg, +	= TOTAL 300 mg
Week 5:	Days 1-7	ZON 300mg, +	= TOTAL 300 mg
Week 6:	Days 1-7	ZON 400mg, +	= TOTAL 400 mg
Week 7-12:	Days 1-42	ZON 400mg, +	= TOTAL 400 mg

Week 13-14: TAPER by 100 mg every 3 days for a total of 2 weeks.

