Exploratory Aim #2: To determine if zonisamide can be prescribed safely and effectively in veterans who are receiving E-CPT-C. Treatment retention as well as side effects will be monitored.

VIII. Inclusion/Exclusion Criteria

Inclusion Criteria:

- 1) Males and females between the ages of 21-65 years old.
- 2) Current alcohol dependence, as determined by a structured clinical interview (Structured Clinical Interview for DSM-IV Axis I Disorders) (SCID) (First et al 1996).
- 3) Current PTSD as determined by a structured clinical interview (SCID) (First et al 1996).
- 4) Veterans with current alcohol dependence, with at least one recent episode of heavy drinking (>4 standard drinks/sessions for men and >3 standard drinks/sessions for women) over the past 14 days.
- 5) Medically and neurologically healthy on the basis of history, physical examination, EKG, screening laboratories (CBC w/ differential, TSH, Free-T4, ASAT, ALAT, GGT, BUN, creatinine, calcium, phosphorous, magnesium, total protein, albumin, electrolytes, VDRL, urinalysis, and for female beta-HCG)
- 6) For women, negative pregnancy test and use of acceptable method of contraception.

Exclusion Criteria:

- 1) Females who are pregnant or lactating.
- 2) Veterans with a current unstable medical condition such as neurological, cardiovascular, endocrine, renal, liver, or thyroid pathology (LFT \geq 3 times normal, abnormal BUN and creatinine, and unmanaged hypertension with BP $>$ 200/120) which in the opinion of the physician would preclude the subject from fully cooperating or be of potential harm during the course of the study (includes those with a history of seizures, glaucoma, prostatic hypertrophy, urethral obstruction, cerebral arteriosclerosis, pyloric stenosis).
- 3) Veterans who meet current SCID criteria for a psychotic disorder or psychosis.
- 4) Veterans taking Clozaril and lamotrigine. Veterans taking more than one anticonvulsant will have an additional blood draw at week 2 to more closely monitor their health.
- 5) Veterans with a history of allergy to zonisamide or hypersensitivity to sulfonamides.
- 6) Veterans already receiving CPT.

IX. Subject Recruitment and Screening

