Initial assessment will include the following measures: (1) Alcohol Dependence Scale (ADS) (Skinner and Allen 1982) is a self-report measure of alcohol dependence consisting of 25 items and will be used to measure the degree of dependence and control for possible group differences in alcohol dependence. (2) Clinical Institute Withdrawal Assessment Scale (CIWA, Ar) (Sullivan et al 1989) is an interviewer driven measure of alcohol withdrawal consisting of 10 items rated on a scale from 0 to 7 and will be used to rule out withdrawal symptoms requiring medical treatment. (3) Demographic information will be collected including contact information and self-designated racial and ethnic data, in accordance with National Institute of Health guidelines.

Study Assessments will include the following: (all measures – except the CAPS which will be used every two weeks - will be administered on each study visit, every week).

(a) The Timeline Follow-Back (TLFB) method (Sobell and Sobell 1992) will be used to document the degree of daily alcohol consumption and to monitor the use of other substances during 12 weeks of treatment.

(b) Obsessive-Compulsive Drinking Scale (OCDS) (Anton et al 1995) will be used to measure alcohol craving throughout the study. The OCDS consists of two subscales and measures obsessive and compulsive thoughts related to drinking.

(c) Clinicians Administered PTSD Scale (CAPS) will be used to obtain data on the frequency and severity of PTSD symptoms and will be administered every two weeks.

(d) Hamilton Depression Scale (HAMD) (Hamilton 1960) will be used to assess the degree and severity of depressive symptomatology. Given the overlap of PTSD and depression this scale will serve as another measure of psychiatric symptomatology.

(e) Posttraumatic Stress Disorder Checklist (PCL-C) will be used to measure PTSD symptoms every week on each visit. The PCL-C is a self-report scale that shares similar

reliability with the CAPS. (Weathers et al 1996)

(f) Modified Version of the Systematic Assessment for Treatment Emergent Events (SAFTEE) will be used to collect information on emergent side effects and their severity (weeks 1-12). This modified version will include, among other side effects, symptoms associated with zonisamide including: fatigue, decreased appetite, dizziness, headache, nausea, and agitation/irritability.

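### The primary drinking models do not say how week-0 drinking enters; a prespecified baseline term uses data already collected, costs 1 to 2% of variance, and may gain precision

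*Combined protocol and SAP*

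**What the plan says.** Section XI, Data Analysis, sets out the primary analysis in a few sentences: "For the primary hypotheses we will use mixed effects models to assess change in alcohol consumption and craving over time", and then "Study medication (zonisamide vs placebo) and time (in weeks and months) will be used as a within-subject factors". No covariate is named. The two primary outcomes, drinks per week and heavy drinking days, are derived from the TLFB. The tested contrast is only implied: "If significant differences between groups are observed Bonferroni adjusted post-hoc tests will be performed to test group differences at each time point".

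Baseline drinking is collected. Section VII (Study Procedures, Overview) lists "collection of baseline assessments of alcohol use, PTSD symptoms and other characteristics", and Table 1 marks both TLFB and ADS at week 0. Of the screening TLFB, Section VII (Initial Assessments/Screening) says "This will allow documentation of the degree and frequency of daily alcohol consumption and smoking pattern", with no look-back window. The only window given is the 14 days of inclusion criterion 4 (Section VIII), which asks for veterans "with at least one recent episode of heavy drinking".

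Two other places give baseline information a role. For the urine biomarker EtG, Section VII describes "Comparison of urine EtG levels during treatment at weeks 4, 8, 12 with baseline values". For the ADS, the initial-assessment text of Section XI says it "will be used to measure the degree of dependence and control for possible group differences in alcohol dependence". The Data Analysis text mentions neither the ADS nor any other covariate.

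**The concern.** An analysis of change over time can treat week 0 in at least four ways: ignore it, subtract it, include it as a repeated response with free arm means, or adjust for it (as a covariate, or as a response with arm means constrained equal). These differ in precision, and the plan does not choose. The primary result would therefore rest on a decision that could be made after the data are seen.

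Entry needs only one heavy drinking episode in 14 days, so baseline drinking may vary widely between veterans. With 3:1 allocation, the placebo arm has about 25 veterans at N=100 and 12 or 13 at N=50. In a trial this small, a few per cent of variance is worth having and a large fraction is worth a sentence in the plan.

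**Working it through.** There is no planned figure to reproduce: the documents give no power calculation, SD, effect size, correlation or alpha.

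**Inputs from the documents.** 12 weekly on-treatment values plus week 0 (Table 1); 3:1 allocation (Section VII, Overview); N=100 (Section VII, Overview; Section IX) or 50 (Section VII, Experimental subjects).

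**Assumptions.** Weekly SD of 1 at every week including week 0, a one-week baseline, a linear model, no dropout, and correlation r of 0.3, 0.5 or 0.7, either equal between all weeks or AR(1).

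**Formulas.** Let V be the covariance matrix of weeks 1–12, b their covariances with week 0, and c a vector of weights 1/12. Up to a common factor for arm sizes, the variance of the 12-week mean difference is:
- week 0 unused: c′Vc
- unconstrained change from week 0: c′Vc + 1 − 2c′b
- baseline-adjusted: c′Vc − (c′b)²

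**One case in full** (equal correlation, r=0.5). c′Vc = (1 + 11×0.5)/12 = 0.542 and c′b = 0.5. Unused: 0.542. Change: 0.542 + 1 − 1 = 0.542. Adjusted: 0.542 − 0.25 = 0.292. Ratio to adjusted: 1.86 for both.

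| Structure, r | Unused | Change | Adjusted | Unused/adjusted | Change/adjusted |
|---|---|---|---|---|---|
| Equal, 0.3 | 0.358 | 0.758 | 0.268 | 1.34 | 2.83 |
| Equal, 0.5 | 0.542 | 0.542 | 0.292 | 1.86 | 1.86 |
| Equal, 0.7 | 0.725 | 0.325 | 0.235 | 3.09 | 1.38 |
| AR(1), 0.3 | 0.146 | 1.075 | 0.145 | 1.01 | 7.4 |
| AR(1), 0.5 | 0.222 | 1.056 | 0.215 | 1.03 | 4.9 |
| AR(1), 0.7 | 0.366 | 0.982 | 0.329 | 1.11 | 3.0 |

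The change score is worse than ignoring week 0 in four of the six cases, equal in one and better in one.

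**Dependence on the contrast.** For a linear trend over weeks 1–12, unused/adjusted is 1.00 at every r under equal correlation (no gain) and 1.02/1.07/1.20 under AR(1).

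**Cost.** With q covariates, variance rises by about (N−3)/(N−3−q). For q=1 this is 97/96 = 1.010 at N=100 and 47/46 = 1.022 at N=50. For q=2 it is 97/95 = 1.021 and 47/45 = 1.044. One covariate breaks even when its correlation with the outcome is √(1/(N−3)): √(1/97) = 0.10 and √(1/47) = 0.15.

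**Net of cost, weakest case** (AR(1), r=0.3). The correlation of week 0 with the 12-week mean is only 0.09. Net variance relative to unadjusted is 1.002 at N=100 and 1.013 at N=50, a very small loss.

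**Form of the covariate.** Week 0 in the response, with arm means constrained equal there, gives the adjusted variance exactly (ratio 1.000 in every case). A weekly model with a single baseline coefficient does so only under equal correlation. Under AR(1) at 0.3/0.5/0.7/0.9 its variance is 1.001/1.012/1.078/1.187 times the optimum. At 0.7 the saving against the unadjusted analysis falls from about 10% (1 − 0.329/0.366) to about 3% (1 − 1.078×0.329/0.366). A baseline-by-week interaction removes the shortfall.

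**Validity.** In simulations of linear models at 75:25 and 38:12, null rejection stayed between 4.7% and 5.2% with no, one or two covariates.

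**The case against.** The strongest objection is that the benefit cannot be quantified from the documents. That stands. The gain ranges from nil to large, depending on a correlation structure and a contrast that the plan does not state. The figures also depend on the unstated baseline window. With an assumed four-week baseline, the change-score ratios become 1.38/1.18/1.08 (equal correlation) and 3.5/3.0/2.3 (AR(1)), while week 0 unused becomes 2.1/3.8/7.8 under equal correlation. So threefold is not an upper bound, and skewed or zero-heavy counts could shift all of these figures.

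It may also be said that analysing change could already mean week 0 in the response with equal baseline means, in which case nothing is lost. That is possible, but the text does not say so, and the same words fit an unconstrained change.

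On the ADS, a reader might infer that the plan contradicts itself or drops the scale. The documents do not support that: the controlling role is stated within the same Section XI, and only the mechanism is missing. Its reference to possible differences also permits a conditional reading. The ADS may add little once baseline TLFB is in the model: a partial correlation of 0.2 saves about 3% of variance at N=100, and 0.1 gives no net gain.

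Finally, the trial calls itself a pilot. That tempers the priority but does not remove the point, because the change is one of wording.

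**Conclusion.** The point holds as one of precision and prespecification. A reader might infer that the unadjusted comparison is biased or that its type I error is inflated. It is not: randomisation protects it, and chance baseline differences are already reflected in its standard error. Nor do the documents support a claim that adjustment is sure to gain.

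What they support is an asymmetry. At assumed correlations of 0.3 to 0.7, ignoring week 0 inflates the variance of the 12-week mean difference by 1–11% (AR(1)) to 34–209% (equal correlation) before the covariate cost, and an unconstrained change score usually inflates it more. Against this, one covariate costs about 1% at N=100 or 2% at N=50. This rests on a one-week baseline with on-treatment variance, roughly normal outcomes and no dropout. The plan should be amended, but its validity does not depend on it.

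**What to change.** In Section XI, Data Analysis, for drinks per week and for heavy drinking days:

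1. Enter the week-0 TLFB value of the same outcome, over a stated pre-treatment window, as a covariate together with its interaction with week, with weeks 1–12 as the response. Alternatively, put week 0 in the response with arm means constrained equal at baseline.
2. Name the medication contrast tested, for example the difference averaged over weeks 1–12.
3. Carry the baseline term into the GEE fallback, and say what happens to it if the nonparametric fallback is used.
4. Secondarily, state how the ADS enters, so that the Data Analysis text agrees with the initial-assessment text, and note that it may add little precision beyond baseline TLFB.

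This is limited to the TLFB outcomes. Section XI applies the same model to craving and PTSD symptoms, but Table 1, as it reads in the text available, shows no week-0 OCDS or PCL-C, so a same-outcome week-0 covariate cannot simply be carried over.

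The cost is wording and a window definition. With complete data, the 12-week mean contrast loses one degree of freedom for the baseline term and one more if the ADS is added. The visit schedule does not change; week-0 TLFB and ADS are already collected, and the window should be one that the screening TLFB covers.
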